## **1 OVERVIEW AND INVESTIGATIONAL PLAN**

### **1.1 STUDY DESIGN AND RANDOMIZATION**

This is a prospective, open-label, multicenter study of patients with Pompe disease who are naïve to treatment with alglucosidase alfa or who have been previously treated with alglucosidase alfa for at least 6 months. Eligible patients will receive one intravenous (IV) infusion of alglucosidase alfa of 20 mg/kg of body weight.

This is a single arm study, no randomization will be performed.

### **1.2 OBJECTIVES**

#### **1.2.1 Primary objectives**

The primary objective of this study is to characterize the pharmacokinetics (PK) of alglucosidase alfa manufactured at the 4000 L scale in patients who have a confirmed diagnosis of Pompe disease.

#### **1.2.2 Secondary objectives**

A secondary objective of this study is to evaluate and explore the relationship between anti-recombinant human acid  $\alpha$ -glucosidase (rhGAA) antibody titers and the PK of alglucosidase alfa.

### **1.3 DETERMINATION OF SAMPLE SIZE**

Approximately 20 patients will be enrolled in this study (10 patients <18 years old and 10 patients  $\geq$ 18 years old). This study is not powered to make any statistical inferences.

### **1.4 STUDY PLAN**

Eligible patients will receive one IV infusion of alglucosidase alfa 20 mg/kg body weight. Prior to the infusion, the patient should be assessed by the Investigator or appropriate designee to determine if the patient is free of acute illness and is clinically stable to receive the infusion. Infusion will be administered in a step-wise manner. It is recommended that the infusion be administered at an initial rate of approximately 1 mg/kg/hr and may be augmented by 2 mg/kg/hr every 30 minutes, if there are no signs of infusion-associated reactions (IARs), until a maximum rate of approximately 7 mg/kg/hr is reached.

Pharmacokinetic and safety assessments will be performed at the scheduled treatment visit. Adverse events (AE) and concomitant medications/therapies will be monitored continuously throughout the study. Patients who are withdrawn from the study will not be replaced (ie, a patient's study number will not be reused); however, additional patients may be enrolled to offset patient dropouts.

An independent Data and Safety Monitoring Board (DSMB) will perform ad hoc reviews of safety data as outlined in the DSMB Charter, which is maintained separately from the study protocol. An immunologist will be consulted, when necessary, to review information and provide treatment recommendations for IARs.

**Table 1 - Schedule(s) of Study Events**

Written informed consent must be obtained prior to any protocol-required procedure.

	Screening	Treatment	Follow Up a
	Visit 1	Visit 2	Call
	(2 days to 4 weeks)	Day 1	Week 4 (≥30 days)
Obtain Informed Consent	X		
Confirm Study Eligibility	X	X	
Demographics, Baseline Characteristics, Medical/Surgical History and Pompe Disease History	X		
Urine Pregnancy Test b	X		
Physical Examination	X		
Weight	X		
Electrocardiogram (ECG)		X	
Serum Chemistry, Hematology, and Urinalysis	X		
IgG and Inhibitory/Neutralizing Antibodies in IgG Positive Patients		X	
Pharmacokinetic Sampling		X c	
Vital Signs		X d	
Infusion		X	
AE Assessment		Continuous Monitoring	
Concomitant Medications/Therapies		Continuous Monitoring	

a The follow-up call represents the last contact for the patient to conduct safety follow up and should occur at least 30 days after the patient's administration of investigational product.

b For female patients of child bearing potential only.

c Pharmacokinetic sampling schedule: pre-dose (prior to infusion); immediately (within a few minutes) before the infusion rate changes from 1 to 3 mg/kg/hr, from 3 to 5 mg/kg/hr, and from 5 to 7 mg/kg/hr; immediately before the end of infusion; and at 1, 2, 4, 8, 12, and 24 hours after end of infusion. In case of IAR, IAR(s) should be appropriately managed and PK sample has to be collected before any first time increase in infusion rate from 1 to 3 mg/kg/hr, from 3 to 5 mg/kg/hr, and from 5 to 7 mg/kg/hr achieved during administration of the remaining dose, immediately before the end of infusion; and at 1, 2, 4, 8, 12, and 24 hours after end of infusion.

d Vital signs (blood pressure, heart rate, respiratory rate, and temperature) will be taken immediately prior to infusion and immediately prior to any infusion rate change, as well as after completion of the post-infusion observation period.

## **1.5 MODIFICATIONS TO THE STATISTICAL SECTION OF THE PROTOCOL**

Not applicable.

## **1.6 STATISTICAL MODIFICATIONS MADE IN THE STATISTICAL ANALYSIS PLAN**

Not applicable.

## 2 STATISTICAL AND ANALYTICAL PROCEDURES

### 2.1 ANALYSIS ENDPOINTS

#### 2.1.1 Demographic and baseline characteristics

The baseline value is defined as the last available value before the patient's administration of investigational product.

All baseline safety parameters are presented along with the on-treatment summary statistics in the safety section ([Section 2.4.5](#)).

##### *Demographic characteristics*

Demographic variables are gender (Male, Female), race (American Indian or Alaska Native; Asian; Black; Native Hawaiian or Other Pacific Islander; White; Not Reported; Unknown), age in years and ethnicity (Hispanic or Latino; Non-Hispanic or Non-Latino).

##### *Medical or surgical history, physical examination*

Medical (or surgical) history includes medical history at Screening of past and/or concomitant diseases or past surgeries.

Abnormal physical examination findings reported by the investigators will be tabulated in data listings in detail.

This information will be coded using the version of Medical Dictionary for Regulatory Activities (MedDRA) currently in effect at Sanofi at the time of database lock.

##### *Disease characteristics at baseline*

Specific disease history includes

- Date of First Symptoms of Pompe Disease.
- Date of Diagnosis of Pompe Disease.
- Duration of treatment on Myozyme (months).
- Pompe Disease cardiovascular, ENT, gastrointestinal, respiratory, and muscular characteristics.
- GAA Gene Mutation.

Any technical details related to computation, dates, and imputation for missing dates is described in [Section 2.5](#).

## 2.1.2 Prior or concomitant medications

Medications and therapies taken by the patient during the 30-day period prior to the baseline evaluation visit and during the course of the study will be recorded in the Concomitant Medication electronic case report form (eCRF)/Concomitant Therapies eCRF. Similarly, pre-infusion medications will be recorded in the Concomitant Medication eCRF and assistive devices will be recorded in the Concomitant Therapies eCRF.

All medications will be coded using the World Health Organization-Drug Dictionary (WHO-DD) using the version currently in effect at Sanofi at the time of database lock.

- Prior medications are those the patient used prior (30 days before baseline evaluation) to first investigational medicinal product (IMP) intake. Prior medications can be discontinued before first administration or can be ongoing during treatment phase.
- Concomitant medications are any treatments received by the patient concomitantly to the IMP, from the time when IMP is administered to study completion or termination. A given medication can be classified both as a prior medication and as a concomitant medication. Concomitant medications do not include medications started during the posttreatment period (as defined in the observation period in [Section 2.1.4](#)).

Any technical details related to computation, dates, and imputations for missing dates are described in [Section 2.5](#).

## 2.1.3 Efficacy endpoints

Not applicable.

### 2.1.3.1 Primary efficacy endpoint(s)

Not applicable.

### 2.1.3.2 Secondary efficacy endpoint(s)

Not applicable.

## 2.1.4 Safety endpoints

The safety analysis will be based on the reported adverse events and other safety information, such as clinical laboratory data, vital signs, ECG, etc.

### *Observation period*

The observation period will be divided into 2 epochs:

- The **prior treatment** epoch is defined as the time from the signed informed consent date up to IMP administration.
- The **after treatment** epoch is defined as the time from the IMP administration to study completion or termination.

The on-study observation period is defined as the time from start of treatment until the end of the study (defined as last protocol planned visit or the resolution/stabilization of all serious adverse events and adverse events with prespecified monitoring).

#### **2.1.4.1 Adverse events variables**

##### ***Adverse event observation period***

- Pretreatment adverse events are adverse events that developed or worsened or became serious from the signed informed consent date up to first administration of IMP.
- Treatment-emergent adverse events are adverse events that developed or worsened or became serious after treatment.

All adverse events (including serious adverse events and adverse events with prespecified monitoring) will be coded to a preferred term (PT), and associated primary system organ class (SOC) using the version of Medical Dictionary for Regulatory Activities (MedDRA) currently in effect at Sanofi at the time of database lock.

The occurrence of adverse events (including serious adverse events and adverse events with prespecified monitoring) is recorded from the time of signed informed consent until the end of the study. Information including a concise description of the event: date and time of event onset and date and time of resolution, determination of seriousness (Yes, No), determination of IAR (Yes, No), severity (Mild, Moderate, Severe), outcome (Fatal, Not Recovered/Not Resolved, Recovering/Resolving, Recovered/Resolved, Recovered with Sequelae/Resolved with Sequelae, Unknown), relationship to treatment (Not Related, Unlikely Related, Possibly Related, Related), action taken regarding treatment (Dose Increased, Dose Not Changed, Dose Reduced, Drug Interrupted, Drug Withdrawn, Not Applicable, Unknown), and other action taken (None, Medication, Non-drug therapy, Hospitalized) is recorded.

Due to the medical significance of any new ventilator use in this patient population, any new use of invasive ventilatory support (not including planned surgical procedures, if total duration of ventilatory support is less than 3 days) will be considered an important medical event and will be reported as an SAE. If a patient requiring ventilatory support becomes ventilator independent, the next instance of invasive ventilatory support (if applicable) will be considered a new SAE.

IARs are defined as adverse events that occur during either the infusion or the observation period following the infusion which are deemed to be related or possibly related to study drug. At the discretion of the Investigator, adverse events occurring after completion of the post-infusion observation period that are assessed as related may also be considered IARs.

#### **2.1.4.2 Deaths**

Death is recorded on the eCRF as an outcome of the AE(s) that resulted in death. In addition, the date of death, cause of death, whether an autopsy was performed, and if yes, autopsy results are also recorded on the eCRF.

### **2.1.4.3 Laboratory safety variables**

Clinical laboratory data consists of blood analysis, including hematology, clinical chemistry, and urinalysis. Clinical laboratory values after conversion will be analyzed in standard international units and international units will be used in all listings and tables.

Blood samples for clinical laboratories will be taken at screening visit unless otherwise specified. The laboratory parameters will be classified as follows:

- Blood Chemistry: sodium, potassium, calcium, chloride, blood urea nitrogen, creatinine, uric acid, alanine aminotransferase, aspartate aminotransferase, total bilirubin, creatine kinase, creatine kinase with MB fraction, lactate dehydrogenase, alkaline phosphatase, total protein, albumin, glucose, phosphorus, gamma-glutamyl transpeptidase
- Hematology: complete blood count with differential and platelets, including hematocrit, hemoglobin, red blood cells, white blood cells, neutrophils, lymphocytes, monocytes, eosinophils, basophils
- Urinalysis: urine color, appearance, specific gravity, pH, protein, glucose, ketones, bilirubin, hemoglobin, urine creatinine, and microscopy if indicated

### **2.1.4.4 Vital signs variables**

Vital signs (blood pressure, heart rate, respiratory rate, and temperature) will be measured at Visit 2 specified in [Table 1](#). Vital signs will be taken immediately prior to infusion and immediately prior to any infusion rate change, as well as after completion of the post-infusion observation period (with a window of  $\pm 30$  minutes for time points after the start of infusion).

### **2.1.4.5 Electrocardiogram variables**

A standard 12-lead electrocardiogram (ECG) will be conducted at Visit 2 as specified in [Table 1](#). The following will be assessed: heart rate, rhythm, RR, PR, QRS, QT, QTc, QRS axis, R voltage V6, S voltage V1, left ventricular hypertrophy criteria, right ventricular hypertrophy criteria, repolarization changes, and overall cardiac impression for each patient. The study site cardiologist should review the ECG in a timely manner for clinical management of the patient. Any abnormal findings that meet the definition of an AE per protocol (1) Section 10.1.1 (eg, that result in an alteration in medical care, diagnostic or therapeutic) will be recorded on the AE page of the eCRF. The Investigator will continue to monitor the patient with additional ECGs until the ECG returns to baseline or the Investigator determines that follow up is no longer necessary.

### **2.1.4.6 Other safety endpoints**

#### **2.1.4.6.1 Routine Anti-rhGAA IgG Antibody Testing**

Serum samples for anti-rhGAA IgG antibody testing will be obtained pre-infusion at the time specified in [Table 1](#).

#### 2.1.4.6.2 *IgG Inhibitory/Neutralizing Antibody Testing*

Serum samples of all IgG seropositive patients will also be tested, as appropriate, for the presence of IgG inhibitory/neutralizing antibodies to alglucosidase alfa.

#### 2.1.4.6.3 *Additional Testing for Moderate, Severe, or Recurrent Infusion-Associated Reactions*

In the event that a patient experiences a moderate, severe, or recurrent IAR suggestive of hypersensitivity reactions, additional blood samples will be collected as described in Sections 2.1.4.6.3.1 through 2.1.4.6.3.3.

##### 2.1.4.6.3.1 Complement Activation Testing

In the event that a patient experiences a moderate, severe, or recurrent IAR suggestive of hypersensitivity reactions, a plasma sample will be drawn within 1 to 3 hours of the event for complement activation testing. Testing also can be initiated at the request of the Sponsor after consultation with the Investigator.

##### 2.1.4.6.3.2 Serum Tryptase Activity Testing

In the event that a patient experiences a moderate, severe, or recurrent IAR suggestive of hypersensitivity reactions, a serum sample will be drawn within 1 to 3 hours of the event for serum tryptase activity testing. Testing also can be initiated at the request of the Sponsor after consultation with the Investigator.

##### 2.1.4.6.3.3 Serum Anti-rhGAA IgE Antibody Testing

In the event that a patient experiences a moderate, severe, or recurrent IAR suggestive of hypersensitivity reactions, the patient should return to the study center no sooner than 3 days following the day of the event to draw a serum sample that will be tested for anti-rhGAA IgE antibodies. Testing also can be initiated at the request of the Sponsor after consultation with the Investigator.

##### 2.1.4.6.3.4 Skin Testing

Skin testing may be performed following consultation with the Investigator, the Sponsor, and, as appropriate, the immunologist appointed to review IAR cases in patients who experience an IAR that meets the following criteria:

- IAR is suggestive of IgE-mediated hypersensitivity reaction, with persistent symptoms of bronchospasm, hypotension and/or urticaria requiring intervention OR any other signs or symptoms at the discretion of the Investigator or the Sponsor.
- Skin testing may be another predictor of IgE-mediated reaction and may be suggested for confirmation of the IgE results.

#### 2.1.4.6.4 Circulating Immune Complex Detection

In the event that a patient exhibits evidence of symptoms suggestive of Immune Complex Disease, serum samples will be obtained for the evaluation of circulating immune complexes in addition to the testing of serum samples that have been archived. The patient will continue to be monitored for immune complex symptomatology, and serum samples will continue to be obtained for the evaluation of circulating immune complexes, as appropriate. Consideration for further evaluation of possible immune complex disease will be at the discretion of the Investigator.

#### 2.1.5 Pharmacokinetic variables

Blood samples will be collected at pre-dose (prior to infusion); immediately (within a few minutes) before the infusion rate changes from 1 to 3 mg/kg/hr, from 3 to 5 mg/kg/hr, and from 5 to 7 mg/kg/hr; immediately before the end of infusion; and at 1, 2, 4, 8, 12, and 24 hours after infusion (times from end of infusion) on Day 1. In case of IAR, IAR(s) should be appropriately managed and PK sample has to be collected before any first time increase in infusion rate from 1 to 3 mg/kg/hr, from 3 to 5 mg/kg/hr, and from 5 to 7 mg/kg/hr achieved during administration of the remaining dose, immediately before the end of infusion; and at 1, 2, 4, 8, 12, and 24 hours after end of infusion. A maximum of 11 blood samples (1 mL each) will be drawn for PK sampling. Per patient, the trial-related blood loss (including any losses in the maneuver) should not exceed 3% of the total blood volume during a period of 4 weeks or 1% at a single time.

Actual dosing and sampling timepoints must be recorded for all days when blood sampling for pharmacokinetics occurs.

From the plasma concentration time data, the following pharmacokinetic parameters will be assessed:

$C_{max}$	The maximum observed concentration
$T_{max}$	The actual sampling time to reach maximum observed concentration
$AUC_{0-last}$	Area under the concentration-time curve from time 0 to the time of the last quantifiable concentration

If data permit,

AUC	Area under the concentration-time curve from time 0 and extrapolated to infinite time
$T_{1/2}$	Terminal elimination half-life
CL	Total systemic clearance
Vd	Volume of distribution

Additional parameters may be analyzed and reported, as appropriate. Industry standard, validated software such as WinNonlin® or Phoenix NLME® will be used for PK data analysis.

### **2.1.6 Pharmacodynamic/genomics endpoints**

Not applicable.

### **2.1.7 Quality-of-life endpoints**

Not applicable.

### **2.1.8 Health economic endpoints**

Not applicable.

### **2.1.9 Further therapy after discontinuation of investigational medicinal product administration during the study**

Healthcare provider will decide what treatment patient will continue to receive after the end of the study (standard of care therapy).

## **2.2 DISPOSITION OF PATIENTS**

Enrolled patients are defined as patients who met the inclusion/exclusion criteria and signed the informed consent.

For patient study status, the total number of patients in each of the following categories will be presented in the clinical study report using a summary table:

- Screened patients.
- Treated patients.
- Patients who did not complete the study treatment as per protocol by main reasons.

For all categories of patients (except for the screened patients) percentages will be calculated using the number of enrolled patients as the denominator.

### **2.2.1 Randomization and drug dispensing irregularities**

Not applicable.

## **2.3 ANALYSIS POPULATIONS**

**Full Analysis Set:** will consist of all patients who received any amount of alglucosidase alfa.

### **2.3.1 Efficacy populations**

Not applicable.

### **2.3.2 Safety population**

Same as full analysis set.

### **2.3.3 Pharmacokinetic population**

Same as full analysis set.

## **2.4 STATISTICAL METHODS**

Data collected in this study will be reported using summary tables, figures and patient data listings. Descriptive statistics will be calculated: n (number of patients with observed results), mean, median, standard deviation (SD), minimum and maximum for the continuous variables and frequencies and percentages and/or shift tables for the categorical variables. No formal inferential statistical tests will be performed.

### **2.4.1 Demographics and baseline characteristics**

Demographic and baseline variables will be presented in patient listings. Summary statistics will be presented for the following variables: age (years), years (since first symptoms of pompe), years (since diagnosis of pompe), Acid  $\alpha$ -glucosidase (GAA) gene mutations, gender, ethnicity/race, weight (kg), height (cm) at baseline.

### **2.4.2 Prior or concomitant medications/therapies**

All medications and therapies reported by the patients during the 30-day period prior to the baseline evaluation visit and during the course of the study will be included in the analysis. Concomitant medications/therapies will be listed by patient. Summary tables giving the frequencies and percentages of the concomitant medications used will be provided.

Medications will be summarized according to the WHO-DD dictionary, considering the first digit of the anatomic category (ATC) class (anatomic category) and the first 3 digits of the ATC class (therapeutic category). All ATC codes corresponding to a medication will be summarized, and patients will be counted once in each ATC category (anatomic or therapeutic) linked to the medication. Therefore patients may be counted several times for the same medication.

The table for prior/concomitant medications will be sorted by decreasing frequency of ATC followed by all other therapeutic classes based on the overall incidence. In case of equal frequency regarding ATCs (anatomic or therapeutic categories), alphabetical order will be used.

### **2.4.3 Extent of investigational medicinal product exposure and compliance**

The actual dose sequence and cumulative dose received over study period will be presented in the patient listing. The cumulative doses will also be summarized within the full analysis set. Compliance to the treatment regimen will be described and summarized in terms of the percentage of scheduled infusions the patient receives.

## **2.4.4 Analyses of efficacy endpoints**

### **2.4.4.1 Analysis of primary efficacy endpoint(s)**

Not applicable.

### **2.4.4.2 Analyses of secondary efficacy endpoints**

Not applicable.

### **2.4.4.3 Multiplicity issues**

Not applicable.

### **2.4.4.4 Additional efficacy analysis(es)**

Not applicable.

## **2.4.5 Analyses of safety data**

All safety analyses will be conducted on the Full Analysis Set.

### **2.4.5.1 Analyses of adverse events**

The table of all treatment-emergent adverse events will be presented by System Organ Class (SOC) and Preferred Term (PT) sorted by the internationally agreed SOC order and decreasing frequency of PTs within SOCs. Multiple occurrences of the same event in the same patient will be counted only once in the tables within a treatment phase.

#### ***Analysis of all treatment-emergent adverse events (TEAE)***

The following treatment-emergent adverse event summaries will be generated for the safety population.

- Overview of treatment-emergent adverse events, summarizing number (%) of patients with any:
  - Treatment-emergent adverse event,
  - Serious treatment-emergent adverse event,
  - Treatment-emergent adverse event leading to death,
  - Treatment-emergent adverse event leading to permanent treatment discontinuation.
- All treatment-emergent adverse events by primary SOC and PT, showing the number (%) of patients with at least 1 treatment-emergent adverse event, sorted by the internationally agreed SOC order and by decreasing incidence of PTs within each SOC. This sorting order will be applied to all other tables, unless otherwise specified.

- All treatment-emergent adverse events by maximal severity, presented by primary SOC and PT, showing the number (%) of patients with at least 1 treatment-emergent adverse event by severity (ie, mild, moderate, or severe), sorted by the sorting order defined above.

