### **6.2.1.1.1 Premature Patient Discontinuation from the Study**

Patients are free to withdraw consent and/or discontinue participation in the study at any time, without prejudice to further treatment. A patient's participation in the study may also be discontinued at any time at the discretion of the Investigator or Sponsor.

The reasons indicated in [Section 8.3.3](#) for withdrawing a patient from treatment may also be justifiable reasons for the Investigator or Sponsor to remove a patient from the study. Patients may be discontinued from the study if the study is terminated by the Sponsor (see [Section 13.5.5](#)).

Patients who are prematurely withdrawn from the study will be asked to complete all assessments prior to withdrawal, if possible. Post-study SAEs will be reported according to [Section 10.3.4](#). A patient will be considered early terminated if the patient does not complete all of the required study visits outlined in the protocol after being enrolled. A patient will be considered discontinued due to an AE if the patient received infusion or partial infusion of the investigational product, but did not complete the study because of an AE, whether or not considered drug related.

At the end of the patient's participation in the study the Investigator will complete the discontinuation electronic case report form (eCRF), documenting the reason(s) for study discontinuation.

In the event that a patient dies, permission will be sought (through a separate informed consent form) from the next of kin for a research autopsy or post-mortem research biopsy. Samples collected from these procedures will be used for research purposes only and data will not be included in any study analyses.

Patients who are withdrawn from the study will not be replaced (ie, a patient's study number will not be reused); however, additional patients may be enrolled to offset patient dropouts.

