## **12.5 Patient Accountability**

Data from all patients who are enrolled in the study will be included in the summary of patient accountability. The frequency and percentage of patients who are enrolled in the study, discontinued from the study, and completed the study, along with reasons for discontinuation, will be summarized.

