### **12.8.3 Adverse Events**

Adverse events, SAEs, and IARs will be coded using the Medical Dictionary for Regulatory Activities and summarized by primary system organ class and preferred term. Detailed listings of patients who experience AEs, SAEs, and IARs will be presented. The incidence of treatment-emergent AEs, IARs, and SAEs will be tabulated (frequencies and percentages) by severity, and by relationship to treatment. Adverse event severity will be categorized as mild, moderate, or severe. In tabulating severity of AEs on a per patient basis, the greatest severity will be assigned to a patient should there be more than one occurrence of the same AE with different reported severities. Relationships of the AE to treatment will be categorized as not related, unlikely related, possibly related, or related. The highest level of association will be reported in patients with differing relationships for the same AE. Listings of AEs, SAEs, and IARs for all patients will be provided, which will include severity and relationship to treatment, as well as actions taken regarding treatment, and patient outcome. A separate listing for patients who withdraw from the study due to AEs will be provided. The incidence of AEs leading to study discontinuations will also be summarized.

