#### ***Analysis of all treatment-emergent adverse event(s) leading to treatment discontinuation***

- All treatment-emergent adverse events leading to treatment discontinuation, by primary SOC and PT, showing the number (%) of patients sorted by the internationally agreed SOC order and decreasing incidence of PTs within each SOC.

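### The SAP reports discontinuation of treatment only, so a patient who leaves the study because of an AE after the single infusion is not shown as an AE discontinuation, as the protocol requires

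*SAP*

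**What the plan says.** **Protocol.** Section 12.8.3 states: "The incidence of AEs leading to study discontinuations will also be summarized". It also promises a listing: "A separate listing for patients who withdraw from the study due to AEs will be provided". Section 12.5 asks for the numbers and percentages of patients enrolled, "discontinued from the study, and completed the study, along with reasons for discontinuation". Section 6.2.1.1.1 classes a patient as discontinued due to an AE if all or part of the infusion was given but the patient "did not complete the study because of an AE, whether or not considered drug related". Section 6.2.1.1 places completion at the Week 4 follow-up call. Section 8.3.3 says that a patient who stops treatment has not thereby left the study.

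**SAP.** The AE overview in 2.4.5.1 has a row for "Treatment-emergent adverse event leading to permanent treatment discontinuation". The matching table is "All treatment-emergent adverse events leading to treatment discontinuation, by primary SOC and PT". Disposition (2.2) has three categories: screened patients, treated patients, and "Patients who did not complete the study treatment as per protocol by main reasons". Sections 1.5 and 1.6, where departures from the protocol would be declared, both read as not applicable.

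**The concern.** The protocol keeps two events apart: stopping treatment and leaving the study. It asks for summaries of the second. The SAP plans summaries of the first only, without saying that anything has changed.

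In a study with repeated dosing the two would largely overlap, because a patient who leaves because of an AE usually also stops treatment. Here there is one infusion. Once it has run, no study treatment remains to be discontinued, yet the patient stays in the study until a call at least 30 days later. A patient who leaves in that interval because of an AE meets the protocol definition and falls outside the SAP rows.

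Two things are at stake. A clinical study report programmed from the SAP could show no AE discontinuations when, on the protocol's definition, there were some. It would also not show how many patients reached the follow-up call, which is the protocol's criterion for completing the study.

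**Working it through.** **1. Length of the infusion.** The inputs are in Protocol 8.1: 20 mg/kg, starting at 1 mg/kg/hr and rising by 2 mg/kg/hr every 30 minutes to 7 mg/kg/hr.

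- First three steps: 0.5 × (1 + 3 + 5) = 4.5 mg/kg in 1.5 h.
- Remainder: (20 − 4.5) / 7 = 15.5 / 7 = 2.21 h.
- Total: 1.5 + 2.21 = 3.71 h.

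This agrees with the protocol's own figure of about 4 hours. Slower steps or interruptions would lengthen it.

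**2. When each rule can register an event.** There is one infusion (SAP 1.1). Therapy afterwards is standard of care (SAP 2.1.9) or commercial product (Protocol 10.6), not study treatment. Treatment discontinuation can therefore occur only while the infusion runs. Study discontinuation can occur at any time up to the follow-up call, at least 30 days after dosing (Appendix A).

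**3. Planned outputs side by side.**

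| Output | Protocol | SAP |
|---|---|---|
| Completed the study | Required (12.5) | No row in 2.2 |
| Discontinued from the study, with reasons | Required (12.5) | No row in 2.2; only non-completion of study treatment |
| AEs leading to study discontinuation | Required (12.8.3) | Not in 2.4.5.1; only treatment discontinuation |
| Listing of AE withdrawals from the study | Required (12.8.3) | Not in 2.2, 2.4.5.1, 2.4.5.2 or 2.4.5.6 |
| Declared departure from the protocol | – | None (1.5, 1.6) |

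**4. A worked case.** Assume that 20 patients are enrolled and treated, and that one, after a complete infusion, leaves on Day 5 because of an AE. The case is hypothetical; the documents give no expected rate.

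- Protocol 6.2.1.1.1: discontinued due to an AE, 1/20 = 5% (1/10 = 10% within that patient's age group).
- SAP 2.4.5.1, both discontinuation outputs: 0/20 = 0%.
- SAP 2.2: the patient is treated and completed study treatment, so nothing shows the departure.
- SAP all-TEAE and severity tables: the event is counted, because the after-treatment epoch runs to study completion or termination (SAP 2.1.4).

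**The case against.** The strongest reply is that little is lost. A treatment-emergent event after the infusion is still tabulated by system organ class, preferred term and severity, and where relevant in the SAE, IAR or death outputs. This stands. A reader might infer that the event vanishes from the tables; the SAP does not support that.

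A second reply is that the SAP, having declared no modification, leaves Protocol 12.5 and 12.8.3 in force. The protocol synopsis speaks of discontinuations due to AEs without saying whether from study or treatment, and SAP 2.2 introduces its table as one of patient study status. This also stands in part: it is an undeclared mismatch, and the documents do not show a decision to drop the outputs. But programmers work from the SAP's list, and the list omits them.

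A third concerns size. A reader might divide 3.71 h by 720 h and infer that nearly all the risk of discontinuation lies outside the SAP rows. That ratio is a share of clock time, not of risk. After the 24-hour PK sample the only routine scheduled contact is a telephone call. Protocol 6.2 and 10.6 also extend follow-up to patients who withdraw, as far as consent allows, so withdrawal need not end safety observation.

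A reader might also want a treated-patient denominator, because the SAP says "Enrolled patients are defined as patients who met the inclusion/exclusion criteria and signed the informed consent" and a dosed but ineligible patient could then push the treated percentage above 100%. That would need an ineligible patient to be dosed after eligibility checks at both visits, and Protocol 12.5 itself bases accountability on enrolled patients. The documents give no reason to change the denominator.

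**Conclusion.** The mismatch is real and should be reconciled. The SAP's discontinuation and disposition outputs do not deliver what Protocol 12.5 and 12.8.3 require. In a one-infusion study they would show zero for an AE discontinuation that the protocol defines and that happens after the infusion ends. Each such patient is worth 1/20 = 5% overall, reported as 0%.

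The consequence is limited to reporting. The study is descriptive, routine safety assessments are not endpoints (Protocol 6.1.2), and no PK analysis changes.

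The conclusion rests on two assumptions.

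- Treatment discontinuation is read as stopping the infusion early. The SAP does not define the term for a single dose; the reading follows from there being only one.
- The event reaches the database. Protocol 10.3.2 collects AEs to study completion or termination, but the opening of Section 10 and Section 10.6 limit new events in the follow-up period to those judged related. Under the narrower rule an unrelated AE that caused withdrawal might not be in the TEAE tables either, which makes a study-discontinuation row more useful.

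**What to change.** - **SAP 2.2:** add two categories, *completed study (follow-up call done)* and *discontinued from study, by reason*. Keep enrolled patients as the denominator, as in Protocol 12.5.
- **SAP 2.4.5.1:** add an overview row, a summary by system organ class and preferred term, and a listing for TEAEs leading to study discontinuation, using the definition in Protocol 6.2.1.1.1. Keep the treatment-discontinuation outputs beside them.
- If the sponsor means to report treatment discontinuation only, declare and justify that in SAP 1.5 or 1.6.

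The cost is a few extra outputs and one data step. The discontinuation eCRF already records the reason for leaving (Protocol 6.2.1.1.1), so the disposition rows are straightforward. The AE fields listed in Protocol 10.4 and SAP 2.1.4.1 record action taken on treatment but no flag that an event led to study discontinuation. The responsible AE must therefore be linked to the reason on the discontinuation form before database lock.
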